The purpose of this Statistical Analysis Plan is to specify the rationale and details of the analysis methods to be used in the clinical trial, entitled “Phase I/II Clinical Trial of Nivolumab (Anti-PD-1 Antibody) in Combination with Local Radiation Therapy for Unresectable Advanced or Recurrent Gastric Cancer Refractory to Standard Therapy”. This Statistical Analysis Plan was prepared in accordance with the Study Protocol of this clinical trial.

2. General matters

2.1 Software used

SAS for Windows ver. 9.4 or R software (version 4.0.3.).

2.2 Significance levels and confidence coefficients

Unless otherwise noted, confidence intervals are two-tailed with a confidence coefficient of 95%.

2.3 Numerical display of results

As a rule, the results of the analysis should be displayed in the formats shown below. Rounding of the displayed value is done by round off.

Minimum value maximum value	Significant digits of data
Average value, quantile	Significant digits of data + 1 digit
standard deviation	Significant digits of data + 2 digits
%	1 decimal place
P-value	3 decimal places; however, if the value is 0.001 or less, it is expressed as “< 0001”.

3. Case handling and analysis population

3.1 Case handling

The principal investigator decides on the handling of cases before the data are fixed, following a review of eligibility and non-compliance with the Study Protocol at the case review meeting.

- 1) All enrolled cases: the population of enrolled patients excluding duplicate enrollments and incorrect enrollments.
- 2) All eligible cases: the population excluding ineligible cases (posterior ineligibility, ineligibility at enrollment, offending enrollment) from all enrolled cases.
- 3) Largest analyzed population (FAS): all eligible patients for whom treatment was administered.
- 4) Safety analysis population: all enrolled cases, those for whom treatment was administered.

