If the above criteria are not met, irradiation is postponed on a day-to-day basis until the criteria are met.

Nivolumab (anti-PD-1 Ab) treatment

Dosage and administration

In accordance with the recommended treatment for unresectable advanced or recurrent gastric cancer, 3 mg/kg (body weight) of nivolumab once every two weeks over at least one hour, or 240 mg once every two weeks over at least 30 minutes, is administered via intravenous infusion.

A total of six administered doses is considered the completion of protocol treatment, but there are no specific provisions for treatment after completion.

Continuation of treatment with nivolumab is also permitted within the insurance coverage at the discretion of the attending doctor.

However, any 'unacceptable concomitant or supportive therapy' as defined in 2.4.3) shall be considered a protocol deviation.

Dosing conditions

All of the following conditions should be met when starting administration of this drug.

- 1) White blood cell count \geq 3,000/ μ L and neutrophil count \geq 1,500/ μ L
- 2) Hemoglobin \geq 9.0 g/dL
- 3) Platelets \geq 100,000/ μ L
- 4) Total bilirubin \leq 2.0 times the upper limit of the institutional reference value
- 5) AST (GOT) and ALT (GPT) \leq 3.0 times the upper limit of the facility reference value. (If liver metastases are present, \leq 5.0 times the upper limit of the institutional reference value.)
- 6) Serum creatinine \leq 1.5 times the upper limit of the facility reference value or creatinine - clearance(Ccr) estimate \geq 60 mL/min.

Basis for setting

It is expected that radiotherapy will enhance the efficacy of anti-tumor immunity. We speculate that the use of nivolumab in combination with post-irradiation therapy may induce an abscopal effect in some cases. We decided to start nivolumab between Days 15-22, with Day 1 as the start date of radiotherapy. Because IFN- γ and TNF- α in serum increased about 10-14 days after irradiation (mouse model) (4), and immune responses such as CTL activation were observed about 2 weeks after administration of peptide vaccines and activated dendritic cells (clinical observation).

A possible disadvantage of this treatment strategy is that the combination of radiotherapy and nivolumab may increase or intensify adverse events; however, as far as we have searched, there have been no reports of serious adverse events occurring.

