2.9. Case registration

(1) Case registration

Case enrollment should take place within 14 days prior to the start of radiotherapy (Day 1).

The attending doctors must obtain written consent based on the subject's own free will from those who meet the eligible criteria based on the inclusion/exclusion criteria. The attending doctors then prepare a case registration form that includes the subject identification number, the date of consent obtained, pre-registration assessment items, and the results of the confirmation of the inclusion and exclusion criteria.

A case registration form is prepared for each registered case and faxed to the research office. Research office: Department of Gastrointestinal Tract Surgery, Fukushima Medical University Hospital. [contact] (The case registration forms in Fukushima Medical University Hospital can use an alternative method to fax.)

The case registration form received by the research office is forwarded to the Data Center, which issues a receipt to the chief investigators at each institution, informing them of the registration number. The receipt form is sent to the principal investigator by fax.

In carrying out the above, the chief investigators at each institution prepare a list of subjects and maintain a list of subject identification numbers and registration numbers.

(2) Diagnostic imaging at registration

After case registration, the chief investigators send the imaging data to the research office as soon as possible. Before the start of radiotherapy, prior consultation is held with the Department of Radiation therapy, Fukushima Medical University Hospital regarding radiotherapy and diagnostic imaging at registration.

(3) Notification upon discontinuation of the study

If a subject enrolled in this study meets any of the following items, a discontinuation contact form is prepared and faxed to the research office.

Withdrawal of consent.

Termination of the study due to death.

Withdrawal from the study.

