2.10. Statistical analysis

(1) Statistical analysis of the evaluation

The composition of the population to be analyzed shall be as follows:

- 1) All enrolled cases: the population of enrolled patients, excluding duplicate enrollments and incorrect enrollments.
- 2) All eligible cases: the population excluding ineligible cases (posterior ineligibility, ineligibility at enrollment, offending enrollment) from all enrolled cases.
- 3) Largest analyzed population (FAS): all eligible cases for whom treatment was administered.

(2) Method of analysis

Primary endpoints

- 1) Disease control rate

For FAS cases, summarize the responses of non-irradiated target lesions in a contingency table, and calculate the cumulative disease control rate and the Clopper & Pearson two-side 90% confidence interval. The disease control rate was defined as the total number of patients with CR/PR/SD divided by the number of eligible patients.

Secondary endpoint

- 1) MST

For FAS cases, estimate the MST using the Kaplan-Meier method, along with a two-sided 95% confidence interval using the Brookmeyer-Crowley method.

- 2) Safety

For all enrolled cases, data regarding AEs and toxicities were tabulated, and the Clopper & Pearson two-sided 95% CI was calculated.

- 3) Local control rate

For FAS cases, summarize the responses of irradiated target lesions in a contingency table, and calculate the cumulative disease control rate and the Clopper & Pearson two-side 90% confidence interval. The disease control rate was defined as the total number of patients with CR/PR/SD divided by the number of eligible patients.

- 4) Immunological parameters

Analyzes are performed at Fukushima Medical University Hospital, Kanagawa Cancer Centre,

and by outsourced testing, as appropriate.

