3.1. Inclusion criteria

Subjects who meet all of the following criteria are eligible in this study.

- 1) Patients with unresectable advanced or recurrent gastric cancer with intolerance or progression after standard treatment (primary and secondary chemotherapy).
- 2) Patients with more than one measurable lesion and with at least one lesion ≥ 2 cm as defined by the RECIST guidelines edition 1.1 on diagnostic imaging (whole-body contrast-enhanced CT or PET-CT) within 14 days before entry.
- 3) Age ≥ 20 years.
- 4) ECOG performance status (PS): 0–2.
- 5) No contraindication for nivolumab (anti-PD-1 Ab) administration.
- 6) No contraindication for radiotherapy.
- 7) The patient's most recent laboratory tests within 14 days prior to enrollment must meet the following criteria. However, if the clinical examination at the time of enrollment is not included within 7 days prior to the first dose of nivolumab, a repeat examination should be performed within 7 days prior to the first dose of the study drug to reconfirm that the most recent clinical examination prior to the first dose of nivolumab meets the criteria below. In all cases, the laboratory values must not have received a G-CSF product or blood transfusion within 14 days prior to the date of testing.

White blood cell count $\geq 3,000/\mu\text{L}$ and neutrophil count $\geq 1,500/\mu\text{L}$

Hemoglobin $\geq 9.0 \text{ g/dL}$

Platelets $\geq 100,000/\mu\text{L}$

Total bilirubin ≤ 2.0 times the institutional standard upper limit (ISUL)

AST (GOT) and ALT (GPT) ≤ 3.0 times ISUL (in case with liver metastasis, ≤ 5.0 times ISUL).

Serum creatinine ≤ 1.5 times ISUL or creatinine clearance (Ccr) estimate $\geq 60 \text{ mL/min}$.

Ccr is calculated by the Cockcroft-Gault formula:

Male Ccr = $\{(140 - \text{age}) \times \text{weight (kg)}\} / \{72 \times \text{serum creatinine level (mg/dL)}\}$

Female Ccr = $0.85 \times \{(140 - \text{age}) \times \text{weight (kg)}\} / \{72 \times \text{serum creatinine level (mg/dL)}\}$

- 8) Patients expected survival ≥ 3 months.

9) Written informed consent is obtained from the patient prior to study enrollment.

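### The primary disease control denominator drops cases of undefined posterior ineligibility, and the plan leaves open whether a patient failing the post-Day 1 laboratory re-test is one of them

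*SAP*

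**What the plan says.** SAP 3.1 builds the efficacy population in steps. From all enrolled cases it forms the eligible set, which is "the population excluding ineligible cases (posterior ineligibility, ineligibility at enrollment, offending enrollment) from all enrolled cases". The FAS is then "all eligible patients for whom treatment was administered". Protocol 2.10 has the same structure and fixes the denominator: "The disease control rate was defined as the total number of patients with CR/PR/SD divided by the number of eligible patients". Neither document defines posterior ineligibility.

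On who decides, SAP 3.1 states: "The principal investigator decides on the handling of cases before the data are fixed". The same sentence says that this follows a case review meeting on eligibility and protocol non-compliance. Protocol 2.2 describes a single-arm, open study.

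Inclusion criterion 7 (Protocol 3.1) sets laboratory thresholds at enrolment. If those tests are not within 7 days before the first nivolumab dose, "a repeat examination should be performed within 7 days prior to the first dose of the study drug to reconfirm" that the thresholds are met.

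The same thresholds appear in Protocol 2.3 as conditions for giving nivolumab. Protocol 2.5 makes failure to meet them, without resumption within 14 days, a reason to discontinue nivolumab. Post-enrolment ineligibility is a separate and open-ended entry in that list.

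SAP 3.2 examines efficacy in the FAS only. SAP 6.5 plans no sensitivity analysis. SAP 8.2 lists the cases excluded from the FAS with reasons.

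**The concern.** An analysis set should be fixed by facts that precede treatment. Here a treated patient can leave the primary denominator on a ground that has no definition and no time limit, and the documents do not say that the people deciding are unaware of response.

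Criterion 7 makes this more than a theoretical gap. It places a test done after irradiation has begun under the heading of eligibility. A patient whose blood, liver or renal values have worsened by then has, on one reading, failed an inclusion criterion. On another reading the patient has met a discontinuation criterion and remains eligible. The first reading takes the patient out of the denominator and the second keeps the patient in.

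The disease control rate is set against a fixed 40%, with no control arm in which the same exclusions would occur. If the patients removed are less likely than the rest to be controlled, the reported rate is too high.

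**Working it through.** **The plan's own figure.** Protocol 2.8 gives a null rate of 40%, an improvement of 20 points (taken as 60%), one-sided 5% and power 80%, and states 39 cases. The arcsine formula gives n = [(1.645 + 0.842) / (2 × (arcsin √0.6 − arcsin √0.4))]² = [2.487 / (2 × 0.2014)]² ≈ 38.1, so 39. The stated figure reproduces.

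**Timing of the re-test.** The criterion 7 tests precede enrolment, and Protocol 2.9 puts enrolment within the 14 days before Day 1. Protocol 2.3 says: "We decided to start nivolumab between Days 15-22, with Day 1 as the start date of radiotherapy". The smallest gap from enrolment tests to first nivolumab is therefore 15 − 1 = 14 days, which exceeds 7. Every patient who reaches nivolumab must be re-tested, at the earliest on Day 15 − 7 = Day 8. That is always after radiotherapy has started. It is usually, though not necessarily, after radiotherapy has ended, because completion is allowed up to Day 14.

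**Two routes for one laboratory failure.**

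| Source | Treatment of the failure | Consequence for the FAS |
|---|---|---|
| Protocol 3.1, criterion 7, read with SAP 3.1 | An inclusion criterion is not reconfirmed | Could be classed as posterior ineligibility and removed |
| Protocol 2.3 and 2.5 | A dosing condition is not met; nivolumab is discontinued if not resumed within 14 days | Remains eligible and treated, so stays |

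No sentence in either document chooses between these.

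**Success rule.** None is stated. From the one-sided 5% design and the two-sided 90% Clopper-Pearson interval (Protocol 2.10, SAP 6.1), I infer success as a lower limit above 40%. At n = 40 this needs 22 controlled (lower limit 40.9%; 21 gives 38.5%). P(X ≥ 22 | 40, 0.40) = 3.9%. The required counts for smaller sets are 22 of 39, 21 of 38, 21 of 37, 20 of 36, 20 of 35 and 19 of 34.

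**Fixed number removed, all uncontrolled, true rate 40% over all 40.**
- One removed: 22 of 39 are still needed, so the error stays at 3.9%.
- Two removed: an observed 16/40 (40.0%) becomes 16/38 (42.1%). The count needed is 21, and P(X ≥ 21 | 40, 0.40) = 7.4%.
- Four removed: 16/36 = 44.4%. The count needed is 20, and the error is 13.0%.

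**Random number removed.** Let each of 40 patients be removed with probability d, and let c be the control rate among those removed. Holding the overall rate at 40%, the rate among those kept is p = (0.40 − d·c)/(1 − d). The error is the sum over k of P(K = k | 40, d) × P(X ≥ r(40 − k) | 40 − k, p), where r(n) is the count needed at size n.

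| d | c | p | One-sided error |
|---|---|---|---|
| 0 | – | 40.0% | 3.9% |
| 5% | 0 | 42.1% | 6.1% |
| 5% | 20% | 41.1% | 4.6% |
| 10% | 0 | 44.4% | 10.5% |
| 10% | 20% | 42.2% | 6.4% |
| 10% | 30% | 41.1% | 4.8% |

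The documents give neither d nor c. Both are assumptions, and c = 0 is the extreme case.

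**The case against.** A reader might infer that the plan contains a built-in path by which patients who deteriorate early are removed from the FAS. The documents do not support that reading. Protocol 2.3 restates the criterion 7 thresholds as dosing conditions. Protocol 2.5 makes failing them a discontinuation reason and lists ineligibility separately, with a changed pathology diagnosis as its example. SAP 5.2 tabulates, within the FAS, incomplete radiotherapy, the number of nivolumab doses and the reasons for stopping. SAP 6.7 plans subgroups by administration status. All of this fits a FAS that keeps early discontinuers.

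A reader might also infer that the principal investigator removes cases knowing their responses. The documents do not say what the case review meeting sees. They say only that it reviews eligibility and non-compliance before the data are fixed. What can be said is that no masking is described.

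Other limits are fair too. Patients who drop out during radiotherapy never reach the re-test. Nothing in the documents shows that those removed would mostly be uncontrolled. The error figures depend on an inferred success rule in a trial positioned as proof of concept. Population counts are tabulated (SAP section 4) and FAS exclusions are listed with reasons, so a reader of the results could see how many were removed and why.

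What stands is that posterior ineligibility is undefined and has no time limit, that Protocol 3.1 and 2.5 can be read to opposite effect, and that no efficacy analysis in all treated patients is planned. Tabulating and listing exclusions shows them but leaves the estimate unchanged.

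**Conclusion.** The point holds as an unresolved ambiguity in the primary analysis set. It is not a mandated exclusion. The plan permits treated patients to be removed from the primary denominator on an undefined, possibly post-treatment ground, and does not say whether a failed pre-nivolumab laboratory check counts as one.

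If uncontrolled patients are removed, the direction of bias favours the treatment. The size depends on how many are removed and on how many of those would have been controlled. At 10% removal the one-sided error ranges from 4.8% (30% controlled among those removed) through 6.4% (20%) to 10.5% (none), against 3.9% with everyone kept. A single exclusion does not raise the error. These figures rest on the inferred success rule and on assumed removal rates. The change is worth making because it is cheap and takes a discretionary element out of the primary result.

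**What to change.** In SAP 3.1 and Protocol 2.10, base the primary disease control rate on all enrolled patients who received at least one radiotherapy fraction. This is close to the safety analysis population that SAP 3.1 already defines. Allow exclusion only for ineligibility facts that existed and were documented before Day 1, and have these judged without access to response data. Report the eligible-only rate as a supplementary result.

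Reconcile Protocol 2.3, 2.5 and 3.1 with SAP 3.1, so that for analysis purposes failing the pre-nivolumab laboratory check is not a ground for removal from the FAS. This concerns only who is counted; it leaves the clinical handling of such a patient untouched. Count these patients as not controlled unless they meet the response rule. The clause in Protocol 2.6 that leaves unevaluable lesions out of the best overall response analysis should be aligned with this, or the same patients could leave the denominator there.

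The cost is protocol and SAP wording. The downside is that the reported disease control rate may be slightly lower.

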3.2 Analysis population

Efficacy is examined in the FAS and safety is examined in the safety analysis population.

4. Examination of test reliability

1) Purpose

Describe the occurrence of major registration violations, discontinuations, drop-outs, etc. in all enrolled cases, and specify the population to be analyzed.

2) Analysis population

All enrolled cases.

3) Analysis items

- (1) Number of cases belonging to the analyzed population.
- (2) Early discontinued or not.
- (3) Any deviations from the Study Protocol.

4) Method of analysis

- (1) Number of cases in the enrolled, eligible, and largest analyzed cohort are tabulated.
- (2) Cases of early discontinuation are tabulated according to reason and institution.
- (3) Cases of deviation from the Study Protocol are tabulated according to reason and institution.
- (4) A list of cases of treatment failure, early discontinuation, and deviations from the Study Protocol is prepared.

5. Comparability considerations

5.1 Demographic items and baselines

1) Purpose

To get an overview of the analyzed population in terms of patient background and baseline.

2) Analysis population

FAS and safety analysis population.

3) Analysis items

Gender, age, presence or absence of allergies, presence or absence of medical history, presence or absence of complications, history of treatment for cancer, general condition (ECOG PS), cancer lesions, organs with cancer, rheumatoid factor (RA), antinuclear antibodies (ANA), SP-D, KL-6, thyroid-stimulating hormone (TSH), free triiodothyronine (free T3), free thyroxine (free T4), tumor markers (CEA, CA19-9).

4) Method of analysis

For continuous quantities, summary statistics (mean, standard deviation, minimum, first quartile, median, third quartile, maximum) are calculated. For categorical data, frequencies and proportions are calculated.

5.2 Treatment status

1) Purpose

Assessing treatment status.

2) Analysis population

FAS.

3) Analysis items

- (1) Number of subjects who do not complete radiotherapy or discontinue radiotherapy by Day 14 and the reasons for those discontinuations.
- (2) During protocol treatment (from the start of radiotherapy to the sixth dose of nivolumab), distribution of the number of doses of nivolumab, distribution of the number of days between doses, and reasons for discontinuation of nivolumab.

4) Analysis methods

- (1) Calculate the completion rate of radiotherapy and determine the frequency of uncompleted treatment by reason of incompleteness.
- (2) Calculate the distribution of nivolumab dosing frequency and the proportion of protocol treatment completed. Calculate the basic statistics of the number of days between doses.
- (3) Prepare a list of the above treatments.

6. Efficacy considerations

6.1 Investigation of primary endpoint

1) Purpose

To explore the efficacy of protocol treatment for unresectable advanced or recurrent gastric cancer, determine the disease control rate of the best overall response, which is SD or better, confirmed by Day 180.

2) Analysis items

Disease control rate of non-irradiated target lesions.

3) Analysis methods

- (1) Construct a waterfall plot for disease control.
- (2) Summarize the responses of non-irradiated target lesions in a contingency table, and calculate the cumulative disease control rate and the Clopper & Pearson two-side 90% confidence interval.

6.2 Investigation of secondary endpoints

6.2.1 Median survival time

1) Purpose

To explore the efficacy of protocol treatment for unresectable advanced or recurrent gastric cancer, determine the median survival time using overall survival defined as the period from the start date of radiotherapy until the date of death from any cause.

2) Analysis items

Survival time from the start date of study treatment to death from any cause.

3) Analysis methods

- (1) Estimate and draw the survival function using the Kaplan-Meier method with log-rank test.
- (2) Estimate of the median survival time is calculated using the Kaplan-Meier method, along with a two-sided 95% confidence interval using the Brookmeyer-Crowley method.
- (3) Estimate of the probability survival rate is calculated using the Kaplan-Meier method, along with a two-sided 95% confidence interval using the Greenwood's formula.

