2.2. Research design

Phase I/II, single-arm, open (non-randomized), prospective study

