2.8. Expected number of cases

40 cases.

Basis for setting

Based on a previous study (ONO-4538-12 study) (5), the disease control rate is set at 40%. At a one-side significance level of 5% and a power of 80%, a sample size of 39 cases are required to detect an additional 20% improvement expected from the study treatment.

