6.4 Adjustment analysis by patient background and baseline

Not conducted in this study.

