6.7 Subgroup and supplementary analyses

The disease control rate and local control rate are analyzed in the same manner as in the main analysis by irradiation site and administration status, etc.

Survival is analyzed in the same manner as the main analysis by completion of study treatment and by irradiation site, etc.

7. Safety considerations

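### The log-rank test in SAP 6.2.1 has nothing to compare in a single-arm trial, and where SAP 6.7 puts it to work, the comparison by treatment completion is biased by immortal time

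*SAP*

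**What the plan says.** Protocol 2.2 describes a "Phase I/II, single-arm, open (non-randomized), prospective study". For overall survival, Protocol 2.10 asks for one thing: "For FAS cases, estimate the MST using the Kaplan-Meier method, along with a two-sided 95% confidence interval using the Brookmeyer-Crowley method".

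SAP 6.2.1, under analysis methods, keeps that median and interval and adds survival probabilities with Greenwood intervals. Its first step, however, is to "Estimate and draw the survival function using the Kaplan-Meier method with log-rank test". It gives no groups, reference curve, null hypothesis, level or sidedness for the test.

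SAP 6.7 then says: "Survival is analyzed in the same manner as the main analysis by completion of study treatment and by irradiation site, etc". Two groupings are named, neither has defined categories, and the list is left open. Neither document has a multiplicity rule or says that subgroup p-values are descriptive. SAP 2.2 mentions significance levels in its heading but sets only an interval convention: "Unless otherwise noted, confidence intervals are two-tailed with a confidence coefficient of 95" per cent.

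**The concern.** A log-rank test compares the survival of two or more groups. A one-sample version compares one group with a stated reference curve. The main survival analysis covers the whole FAS, which is one group, and no reference curve is given, so the instruction cannot be carried out where it stands.

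It does take effect in SAP 6.7, which borrows the main method. Every patient there is assigned the same treatment, so no such p-value can show whether radiotherapy adds to nivolumab, which is the trial's question. The two named groupings also differ in kind. Irradiation site can be fixed at Day 1, although Protocol 2.3 chooses the lesion by symptoms or size, so sites may differ in prognosis. Completion of treatment is known only about three months after the survival clock starts. Patients who die early become non-completers by definition, and the test counts that as a survival difference.

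At stake is a survival p-value that looks like evidence and is largely built in. Protocol 1.1 intends this trial to supply basic data for later randomised trials.

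**Working it through.** **1. Can the test run in the main analysis?** With one group, observed deaths equal expected deaths at every death time. The numerator is 0 and the variance is 0, so the statistic is 0/0. A trial run on 40 simulated patients in one group returned no value. Protocol 2.6 does mention groups divided at the median survival time, but for the immunological analyses. Those groups are defined by survival itself, so they cannot serve as the missing comparison.

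**2. Which significance level applies?** The only stated level belongs to the primary endpoint (Protocol 2.8), where "the disease control rate is set at 40" per cent and "At a one-side significance level of 5% and a power of 80%, a sample size of 39 cases are required to detect" a 20-point gain. That figure reproduces with the arcsine formula: [(1.645 + 0.842) / (2·asin√0.6 − 2·asin√0.4)]² = 38.1, rounded up to 39. It says nothing about survival tests. A two-sided 5% per log-rank test is therefore assumed below.

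**3. When is completion known?** Protocol 2.1 starts nivolumab on Day 15–22 and gives six doses two weeks apart. With no delays the sixth dose falls between Day 15 + 5×14 = 85 and Day 22 + 5×14 = 92. SAP 6.2.1 counts survival from the start of radiotherapy, Day 1. Protocol 2.5 lists death during protocol treatment as a reason for discontinuation, so any death in this window creates a non-completer.

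**4. How large is the resulting bias?** Assumptions: 40 patients; exponential survival with median 6 or 13 months (the background range in Protocol 1.1, which describes chemotherapy); 30 months of uniform accrual and follow-up of about 12 to 42 months (Protocol 2.11); 20% or 40% of patients stopping for reasons unrelated to survival; and no effect of completion on survival. With a 6-month median (6 × 30.44 = 182.6 days), survival to Day 85 is 0.5^(85/182.6) = 0.72, so about 11 of 40 patients die too early to complete. With a 13-month median (395.7 days) it is 0.5^(85/395.7) = 0.86, so about 6 of 40 do.

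Share of simulated trials rejecting at nominal 5% (4,000 trials per cell):

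| Median OS | Completion day | 20% stop otherwise | 40% stop otherwise |
|---|---|---|---|
| 6 months | 85 | 80% | 47% |
| 6 months | 92 | 83% | 52% |
| 13 months | 85 | 50% | 23% |
| 13 months | 92 | 52% | 25% |

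A separate run gave 49–81% (6 months) and 22–49% (13 months), within three points of the table at each end. If death is the only thing that prevents completion, every simulated trial rejects. A random split of the same patients rejects in about 6%.

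**5. How much does multiplicity add?** Ignoring the completion bias, two independent tests give 1 − 0.95² = 9.8%. If their statistics correlate at 0.8, simulation gives 7.8%. Further groupings raise the figure: for example, five independent tests give 1 − 0.95⁵ = 22.6%. The documents fix no number beyond the two named.

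**6. What could a sound split detect?** With all 40 patients dead and a 1:1 split, the hazard ratio detectable with 80% power is exp[−(1.960 + 0.842)/√(40 × 0.25)] = 0.41.

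**The case against.** The strongest defence is that the phrase in SAP 6.2.1 was meant for the subgroup curves in SAP 6.7 and is only misplaced. Survival is a secondary endpoint, SAP 6.2.1 states its purpose as exploring efficacy, SAP 6.7 is headed as subgroup and supplementary work, and no decision depends on a survival p-value. With no confirmatory claim, there is no formal family-wise error rate to protect. SAP 6.4 says of covariate adjustment "Not conducted in this study", which is defensible with 40 patients.

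Most of this stands, and it rules out several stronger readings.

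- A reader might infer that every survival p-value would come from an unplanned contrast. SAP 6.7 names two groupings in advance; only those added under its open ending would be unplanned.
- A reader might infer that the main analysis will yield a p-value. With one group it yields none, and SAP 6.2.1 does not tell the analyst to invent a split.
- A reader might infer that the two named tests must nearly double the 5% error rate. At correlation 0.8 the factor is 0.078/0.05, about 1.6.
- A reader might infer that a subgroup p-value will shape the next trial. Protocol 1.1 speaks of median survival and local control, not of subgroup tests.

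What the defence does not answer is the completion comparison. It is named in advance, yet it is biased even if it is the only test run, and an exploratory label does not remove the bias.

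**Conclusion.** Wrong as written, in a limited part of the plan. The log-rank test in SAP 6.2.1 is undefined for one group without a reference curve, and it departs from Protocol 2.10. Carried into SAP 6.7, it gives a completion comparison that, with no true effect, would reject in roughly 22–81% of trials instead of 5%. That range depends on the assumptions in step 4 of the working, above all the median survival and the share stopping for other reasons. Sicker patients stopping early, which the simulation leaves out, would be a further source of bias. The multiplicity issue is smaller: about 8–10% for the two named groupings (correlation 0.8 to 0, two-sided 5% assumed), and more for any added.

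A reader might go on to doubt the survival results as a whole. The documents do not support that: the Kaplan-Meier median, its Brookmeyer-Crowley interval, the Greenwood intervals and the primary endpoint do not use the test.

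**What to change.** - **SAP 6.2.1, analysis method (1):** delete *with log-rank test*, so that the section matches Protocol 2.10.
- **SAP 6.7, list:** remove *etc.* so that the groupings are closed.
- **SAP 6.7, irradiation site:** define the categories and fix them at Day 1. Label any log-rank p-value exploratory and not evidence of a treatment effect.
- **SAP 6.7, completion:** report no log-rank p-value and draw no curves from Day 1. Give survival estimates only from a landmark at about the planned sixth dose, among patients alive then and grouped by their status at that time, or treat completion as a time-dependent variable. Describe the result as descriptive, since patients who stop may be sicker.

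The cost is a few lines of SAP text, with no new data or patients. Fewer survival p-values can be reported, which loses little given how large a difference 40 patients would need to show. The landmark analysis leaves out early deaths, so report their number beside it.
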